| Study Design | Co-Primary Objective, Acute Pain: To determine whether multimodal M-Stim reduces Pain Intensity 30% more than TENS in the first 10 days after presenting for treatment. Co-Primary Objective, Chronic Pain: To determine whether multimodal M-Stim reduces disability 30% more than TENS at 6 months. A randomized, double-blind controlled trial with 3- (aLBP) or 6- month (cLBP) follow-up. |
|-------------------------|--|
| Study Setting | The study will be conducted at mixed physical therapy/chiropractic practices in Washington, DC, Maryland, and Virginia, which offer demographic and economic diversity. These clinics provide an ideal environment, with frequent follow-ups and ongoing therapy but no onsite access to opioid prescribers. |
| Eligibility Criteria | Inclusion Criteria: - Male or female adults aged 18-90 presenting for treatment of acute or chronic low back pain - Self report of moderate to severe LBP of 4 or greater out of 10 on a 0-10 Numeric Rating Scale. - Acute: pain duration <3 months not using opioids for the current exacerbation of low back pain - Chronic: Pain duration >= 3 months with or without ongoing opioid use - Capacity to understand risks and benefits (informed consent). - Smartphone for Qualtrics web-based platform use Exclusion Criteria: - Radicular pain likely reflecting a surgical or mechanical problem - Inability to apply or use the device - Sensitivity to cold or vibration (e.g Raynaud's or Sickle Cell Disease) - Diabetic neuropathy rendering a patient unable to determine if the device is too hot - New neurologic deficits, skin lesions over the low back area - A contraindication to any medication for pain management that would impact analgesic use record |

| | - Pacemaker |
|--------------|---|
| Intervention | The experimental arm DuoTherm is a novel multimodal low back pain relief device incorporating 8 harmonic vibration patterns of mechanical stimulation (M-Stim) including neuromodulatory frequencies, 5 intensity levels, and optional heat, cold, and pressure delivered through a sculpted metal plate attached with a belt and controlled by buttons on the belt. Patients will be instructed to use the device at least daily for 30 minutes. The active control is a prescription 4-lead 8-channel TENS unit (LG Smart) with variable intensity. |

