| | Participants will be instructed to use the device for a minimum of 30 minutes a day. Both M-Stim and LG Smart TENS groups will receive a standard pain management regimen typically used for low back pain standardized across all clinicians participating in the study. Participants will keep the devices and be instructed to use them for pain as needed during the duration of the study. |
| Outcomes | Opioid Use Primary Outcome: |
| | Prior use: For patients with prior or ongoing opioid use, a 30% reduction in MME (Milligram Morphine Equivalents) between the first 14 days and the last 14 days of daily diary recordings using the DOSE data collection tool. |
| | Opioid naïve: 30% reduction of those receiving an opioid prescription "prescribed to me for this event" |
| | Secondary outcomes: Use days; total MME and use past 7 days in the opioid naïve; use days by those with more severe pain using the NIH Research Taskforce definitions; and prescribing compared to a contemporaneous national LBP population (25%). |
| | Pain Primary Outcome: |
| | Chronic: 30% lower disability at 6 months using PROMIS Pain Interference for those with ongoing pain >3 months |
| | Acute: 30% lower NRS 0-10 "pain now" from entry to 10 days for those presenting with an episode of pain starting within the past 2 weeks |
| | Secondary Outcomes: Change in disability for those with >=57.7 PROMIS Pain Interference; restoration of function to normal (PI=50); |

| | integrated analysis with | n common | criteria fo | r restoration | on of function | on with | |
|-------------------------|---|---------------|--------------------|---------------------|----------------------|----------------------------|--|
| | multifidus stimulation s | surgery. | | | | | |
| | | | | | | | |
| Participant Timeline | | Initial Visit | Daily x 28 days | Weekly for 3 months | Monthly for 3 months | Monthly 4 - 6 months | |
| | Consent, Enrollment, Randomization | ALBP, CLBP | | | | | |
| | Minimum Dataset, Pain Catastrophizing Sullivan, PROMIS Depression, Physical Function | ALBP, CLBP | | | | | |
| | NRS (at that moment & past 24 hours) | ALBP, CLBP | ALBP, CLBP | ALBP, CLBP | ALBP, CLBP | CLBP | |
| | NRS after 30 minutes | ALBP, CLBP | | | | | |
| | NRS Past week | | | ALBP, CLBP | ALBP, CLBP | CLBP | |
| | NRS Past month | | | | ALBP, CLBP | CLBP | |
| | PROMIS Pain Intensity, Pain Interference | ALBP, CLBP | | ALBP, CLBP | ALBP, CLBP | CLBP | |

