| | Dose, Opioid formulation, number Source (DOSE tool), other analgesics | ALBP, CLBP | ALBP, CLBP | ALBP, CLBP | ALBP, CLBP | CLBP | |
| | Device usage | | ALBP, CLBP | ALBP, CLBP | ALBP, CLBP | CLBP | |
| Sample Size | To estimate the M-Stim | interventi | on effect : | size, a retro | spective st | udy of | |
| | 59 cLBP patients on ch | ronic opioi | ds (100% | prolonged | opioid use) | | |
| | reported a 28% reducti | on in MME | after spin | al stimulat | or | | |
| | implantation,[40] reducing MME 26.2(SD32.8) compared to 5.8(SD34.2) | | | | | | |
| | for those with conventional treatment (effect size 0.60. A priori, we would | | | | | | |
| | be able to detect an effect size of 1 (meaning a difference of 1 standard | | | | | | |
| | deviation) with 94% power and alpha of .03 using a Wilcoxon Mann | | | | | | |
| | Whitney test with 30 in each group. With this effect size for a two-sided | | | | | | |
| | significance of 0.05, 17 participants per group would detect a 30% | | | | | | |
| | prescribing reduction, while 50 participants on chronic opioids per | | | | | | |
| | treatment group would provide 85.4% power to detect a 30% reduction in | | | | | | |
| | MME. Given the 20% in a previous study by Jamieson et al, we increased | | | | | | |
| | the cLBP sample to 50 | - | | Jannoson | icat, we iiio | ioasea | |
| | | | | | | | |

| | We planned to recruit 60 aLBP participants who had never taken opioids for their back pain, and 100 cLBP without a new prescription but with or without chronic opioid for cLBP. |
|----------------------------|--|
| Recruitment | Patients were recruited from Kaizo Health Centers in Landover and Fairfax, through direct referrals, flyers, and digital content like social posts and emails targeting local populations. Flyers were also distributed at three local pain clinics. |
| Randomization | After eligibility screening and informed consent, a 4-digit participant ID and the intervention allocation were randomly assigned by the survey software to either the DuoTherm or LG Smart TENS group within acute and chronic arms. A copy of the informed consent was emailed to the participant. |

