monthly surveys added past month NRS, Blinding assessment for additional 3 months for those started in chronic strata. Added "source" for each opioid use case to DOSE tool collecting opioid formulation, dose, and number of pills. We intended to use evaluate change in MME over time for chronic opioid users. The FDA recommended requiring participants on opioids maintain dosage and frequency. As we did not have access to prescribing records, and opioid reduction was a desired outcome measure, we evaluated opioid use for the first two weeks versus the last two of those endorsing prior opioid use. We extended the baseline and follow-up Pain Intensity measurements to one month rather than one week. 3a) 8/31/22 – Site Visit. PI noted staff using "will not fit" criteria rather than BMI of 30 from pilot study. New device fits variable BMI, based on abdominal girth. Retained "if device fits", exclusion criteria using BMI changed to BMI >50, noting controversy in using BMI as exclusion criteria. 4) 5/5/23; Added "Do you think you will need surgery" and "do you think you will need epidural" questions, and "did you get surgery" and "did you get an epidural" to monthly. 5) 7/13/2023 New Location added Stratification by chronicity versus opioid use status: enrollment strata were based on verbal endorsement of duration and no acute opioid use for back pain. Initial evaluation of registration data after enrollment was complete revealed 16 of 60 in the "acute" strata reported a duration longer than three months, and half in each chronicity strata no prior opioids for LBP. In consultation with Clinical Trials.gov, we pooled the data and included both opioid and pain outcomes as a single NCT04491175 registry with two different publications and analyses. Informed Informed consent will be obtained from each participant after screening. Consent Participants will be informed about the voluntary nature of the study, with a HIPAA form for confidentiality. Consent will be documented via selecting 'continue' on the digital consent form. Confidentiality Patient data will be stored on password-protected network drives. All data will be de-identified using a unique study ID for each participant. Confidential records will be stored in secure, restricted-access rooms. Declaration of The principal investigator has financial conflict of interest from design interests and research into the DuoTherm device, and creating a company to

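### Opioid-naive, prior and current use are defined differently across sections, so past-only users fall under the MME-reduction primary outcome and outside the primary prescribing outcome

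*Combined protocol and SAP*

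**What the plan says.** All places are in the combined protocol and SAP.

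- **Sample Size** plans "60 aLBP participants who had never taken opioids for their back pain" and 100 chronic participants with or without chronic opioids. The 85.4% power for MME is stated for 50 per group, all on chronic opioids.
- **Eligibility Criteria** admit to the acute stratum on a narrower condition: "Acute: pain duration <3 months not using opioids for the current exacerbation of low back pain". The chronic criterion is "Chronic: Pain duration >= 3 months with or without ongoing opioid use".
- **Outcomes** splits the opioid primary outcome in two. One part reads "For patients with prior or ongoing opioid use, a 30% reduction in MME", comparing the first and last 14 days of the daily diary. The other, for opioid-naive participants, is the proportion given a prescription for this event.
- **Protocol Amendments** says strata were formed on verbally reported duration and no acute opioid use. After enrolment closed, 16 of the 60 in the acute stratum were found to have reported a duration above three months, and "half in each chronicity strata no prior opioids for LBP". It describes the two-window MME comparison as made in participants reporting earlier opioid use.
- **Statistical Methods** runs the paired t-test on the two windows in participants who took opioids at some point during the trial.

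**The concern.** The acute criterion cannot deliver the planned population: someone who took opioids for an earlier episode is eligible. The outcome rule then treats that person as a prior user. The same happens to a chronic participant who once took opioids for back pain but no longer does.

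Two things follow for past-only users. They enter an outcome meant to measure a fall from established use, which they may not have. And if they are newly prescribed an opioid, which the trial aims to prevent, that event lies outside the primary prescribing outcome.

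The analysis population is also unsettled. Outcomes and Protocol Amendments use reported earlier use. Statistical Methods uses opioid intake during the trial, which is known only after randomisation and may be affected by the device. That set drops past users who stay opioid-free, and under the Outcomes rule they are not in the naive outcome either. With several definitions standing, the population of a primary analysis can be chosen after the data are seen.

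**Working it through.** **1. Side by side.**

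| Section | Condition used |
|---|---|
| Sample Size, acute | never took opioids for back pain |
| Eligibility, acute | none for the current exacerbation |
| Outcomes, MME | earlier or continuing use |
| Outcomes, prescribing | opioid-naive |
| Protocol Amendments, MME | reports earlier use |
| Statistical Methods, paired test | took opioids during the trial |

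A past-only user meets the second, third and fifth conditions, fails the first and fourth, and meets the sixth only if use restarts. No section says what to do when MME in the first window is zero.

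**2. What the MME outcome does with such a person.** Percent reduction is 100 × (M1 − M2)/M1, where M1 and M2 are MME in the first and last 14 diary days.

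- *Scored per person:* M1 = M2 = 0 gives 0/0. M1 = 0 with later use gives a division by zero. A past user newly prescribed in days 1–14 who then stops has M1 > 0 and M2 = 0, and counts as a 100% reduction.
- *Scored as a group mean:* zero-change participants pull both arm means towards zero, and the newly prescribed person who stops adds a favourable difference.

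**3. How many.** Assume planned enrolment and take the reported half as exact.

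- Acute stratum with prior use: 0.5 × 60 = 30. If all 16 with longer duration were prior users, 30 − 16 = 14 truly acute prior users remain; if none were, 30. Range 14 to 30.
- Chronic stratum with prior use: 0.5 × 100 = 50. The split between current and past-only is not given.

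**4. The stated power, reproduced.** From Sample Size, MME falls by 26.2 (SD 32.8) against 5.8 (SD 34.2).

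d = (26.2 − 5.8)/√((32.8² + 34.2²)/2) = 20.4/33.51 = 0.609

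A two-sample t-test with 50 per arm and two-sided alpha 0.05 (noncentrality 0.609 × √(50/2) = 3.04) has power 85.4%, as stated. The figure is arithmetically sound for an all-current-user population.

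**5. Dilution.** Let a share f of each arm have exactly zero change, and q = 1 − f. Each arm then has mean qμ and variance q(σ² + μ²) − (qμ)². For f = 0.25:

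- means 19.65 and 4.35, difference 15.30
- variances 0.75 × (32.8² + 26.2²) − 19.65² = 935.6 and 0.75 × (34.2² + 5.8²) − 4.35² = 883.5
- d = 15.30/√((935.6 + 883.5)/2) = 15.30/30.16 = 0.507

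| f (assumed) | d | Power, 50 per arm |
|---|---|---|
| 0 | 0.609 | 85.4% |
| 10% | 0.57 | 80.4% |
| 25% | 0.51 | 70.9% |
| 50% | 0.40 | 50.7% |

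**6. Restriction to current users.** If all 50 chronic prior users are current users and split evenly, there are 25 per arm. Power is 55.9% at d = 0.609 (54.7% at d = 0.60). For the chronic stratum this is the most favourable count under step 3.

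**The case against.** The best reply starts from Statistical Methods. A paired t-test compares mean MME and computes no individual percentages, and its restriction to people who took opioids during the trial removes those with none in either window. A reader might infer that every past-only user has an undefined result, or that the trial scores a new prescription followed by stopping as a success. The documents do not support that as a general statement: it holds only if the 30% is a per-person criterion, which no section says. What remains is dilution or distortion of a mean, and a restriction that conflicts with two other sections and selects after randomisation.

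A reader might also infer that 30 of 80 prior users (30/(30 + 50), about 38%) start from zero by eligibility. That does not follow. The first window comes after randomisation, eligibility bars opioids only for the current exacerbation, and the DOSE sources include prescriptions for another event, so early MME can be above zero. The figure also ignores the 16 with longer duration and treats no chronic prior user as past-only. The true share could lie on either side.

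Nor are prescriptions to past-only users shown to be ignored everywhere. The prescribing relative risks in Statistical Methods are not expressly limited to naive participants; the exclusion is from the primary outcome as defined.

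Finally, the sponsor discloses how strata were formed and what was found. That is fair, and makes the planned acute count partly a matter of record. It does not supply a common definition or a zero-MME rule.

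**Conclusion.** The concern stands as a definitional inconsistency affecting who enters each primary opioid analysis. Planned population, eligibility, outcome rule and analysis set use different conditions, and past-only users in both strata are assigned to an outcome that may not fit them.

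Its size cannot be fixed from the documents. The pool is about 30 acute-stratum prior users (14 to 30 truly acute) plus an unknown part of about 50 chronic prior users, assuming planned enrolment and an approximate half. The power losses are illustrations: the zero-change shares are assumed, and the 25 per arm assumes an even split with every chronic prior user still taking opioids. The 85.4% is not miscalculated; it describes a population that the eligibility criteria do not require.

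**What to change.** - Adopt one baseline definition of naive, past-only and current use, and carry it through Eligibility Criteria, Outcomes, Sample Size, Statistical Methods and Protocol Amendments. Correct the never-user wording for the acute stratum.
- Classify by opioid use at entry from the initial-visit DOSE record, with the prior-use report alongside. Those not using at entry go to the new-prescription outcome; those using at entry go to the MME outcome.
- Compare MME between arms in that baseline-defined set, not in those who took opioids during the trial. State whether the 30% applies per person or to the group, and how zero first-window MME is handled.
- Restate power for the resulting set sizes.
- Fix the flag before unblinding, or label the analysis post hoc. Either way, disclose that enrolment was complete and registration data had been examined. Report the current Outcomes classification as a sensitivity analysis.
- Adjustment for stratum and ever-use is optional, where the number of events allows.

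The cost is SAP wording and a flag derived from data that the Participant Timeline already schedules. The price is a smaller MME set with lower stated power. Because randomisation was within acute and chronic arms only, balance by use at entry is not guaranteed.

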Participants recorded when they used their device, duration of use, and any additional pain relief modalities (exercise, stretching, bath, hot tub, therapy, massage). Patients were asked to record any thermal use or therapy cycle or channel as appropriate to their device.

Participants verbally endorsing pain for less than three months (acute) were entered into a 3 month follow-up program, or 6 months (chronic) for those for whom back pain had been an ongoing problem for more than 3 months.

Statistical Methods

Statistical analysis was performed with masked intervention allocation by a statistician new to the project to determine differences in primary and secondary outcomes.

An intention-to-treat analysis included all participants meeting inclusion criteria. Summary statistics (means, standard deviations, proportions) were calculated using T-tests and Chi-squared tests. Opioid prescribing differences were calculated with raw percent of change and relative risks. Diary entries and item-level data were analyzed for missing data to assess the need for imputation. Relative risks were calculated for MME and opioid use days between intervention groups, with paired T-tests used to compare first two and last two weeks of MME in those who used opioids during the study. A linear regression assessed BMI's interaction with opioid use, calculating marginal effects with standard errors via the Delta Method. Data analysis was performed using STATANow/SE 18.5.

For pain outcomes, in addition to the above methods, missing 10 day NRS-1 data will be imputed using forward fill and KNN. A neural network will be created to determine factors contributing to 13 week Pain Interference, with iterative modeling to reduce mean absolute error. Graphs with r-squared for predictors will be generated.

| Data Monitoring | Data collection was conducted through an app that tracked daily pain, opioid use and device usage. Monitoring included weekly enrollment review by the protocol statistician to assess comprehension of the data collection tool. Adverse events were reported as per protocol. | |
|------------------------|---|--|

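### No between-arm opioid method uses the randomised acute/chronic stratum or adjusts for prior opioid use, so pooled comparisons, above all use days, are open to chance imbalance in prior users

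*Combined protocol and SAP*

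**What the plan says.** All references are to the combined protocol and SAP.

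- **Randomization.** The survey software allocated participants "by the survey software to either the DuoTherm or LG Smart TENS group within acute and chronic arms". Prior opioid use is not named as an allocation factor.
- **Sample Size.** "We planned to recruit 60 aLBP participants who had never taken opioids for their back pain", together with "100 cLBP without a new prescription but with or without chronic opioid for cLBP". The acute stratum was therefore meant to be free of opioid history.
- **Protocol Amendments, closing note on stratification.** "Initial evaluation of registration data after enrollment was complete revealed 16 of 60 in the" acute stratum with pain lasting more than three months, and "half in each chronicity strata no prior opioids for LBP". The data were then pooled.
- **Outcomes.** One primary opioid outcome is MME change in people with prior or ongoing use. The other is receipt of a prescription in the opioid-naive. The secondary list opens "Secondary outcomes: Use days; total MME and use past 7 days". The limit to opioid-naive participants follows the second item; use days, separated by a semicolon, has none.
- **Statistical Methods.** The population is everyone who met the inclusion criteria. "Opioid prescribing differences were calculated with raw percent of change and relative risks". MME and use days are also compared by relative risk between the device groups. Paired t-tests of early against late MME are run in people who took opioids on study. The only regression on opioid use concerns BMI. Neither the stratum nor prior use appears as a factor, covariate or subset.

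**The concern.** The acute/chronic stratum was expected to separate people by opioid history and did not: about half of each stratum had prior opioids. Balance in prior use between arms was therefore left to chance. In a comparison that pools prior users and naive participants, a surplus of prior users in one arm raises that arm's opioid use whatever the device does. The crude ratios in Statistical Methods cannot separate the two.

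Two further losses follow. Leaving out a factor used in the randomisation, and a recorded baseline factor that probably predicts the outcome, gives up precision. And because Statistical Methods does not repeat the subsets set out under Outcomes, a reader cannot tell which opioid ratios are pooled. The paired MME set adds to this: it is chosen by use after randomisation, whereas Outcomes and the 6/8/2022 amendment choose it by prior use.

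**Working it through.** **The plan's own figure.** The plan gives no figure for imbalance. Its nearest figure is 85.4% power for MME with 50 chronic opioid users per group, and it reproduces: d = (26.2 − 5.8)/√((32.8² + 34.2²)/2) = 20.4/33.5 = 0.609, and a two-sided 5% t-test with 50 per group has 85.4% power. That calculation lies wholly within opioid users and uses no stratum, so it neither supports nor contradicts this point.

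**Inputs from the documents.** 60 + 100 = 160 participants planned; about half in each stratum with prior opioids, so about 80 prior users.

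**Assumed.** 1:1 allocation with 80 per arm. The ratio is not stated, but Sample Size works with equal groups ("Whitney test with 30 in each group. With this effect size for a two-sided"). Opioid-use rates are also assumed, because the documents give none.

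**Step 1: size of chance imbalance.** The number of prior users in one arm is hypergeometric (160 participants, 80 users, 80 drawn).

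- SD of the count = √(80 × 0.5 × 0.5 × 80/159) = 3.17.
- If one arm has x users the other has 80 − x, so the difference in share is 2(x − 40)/80, with SD 2 × 3.17/80 = 7.9 points.
- Exact balance within strata changes little: counts with SD 1.95 (acute) and 2.51 (chronic) combine to √(1.95² + 2.51²) = 3.18, or 8.0 points.
- 10 points or more (36 v 44 users or worse): 26.8%. 15 points or more (34 v 46 or worse): 8.2%. Both are two-sided; by symmetry half of each, about 13% and 4%, would favour DuoTherm.

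**Step 2: effect on a pooled use-day ratio with no device effect.** Ratio = [lo·pu + (1 − lo)·pn]/[hi·pu + (1 − hi)·pn]. Here pu and pn are the assumed shares of days with use in prior users and naive participants, and lo and hi are 0.5 minus and plus half the imbalance.

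| Imbalance | pu 30%, pn 3% | pu 30%, pn 10% |
|---|---|---|
| 10 points | 0.1515/0.1785 = 0.85 | 0.190/0.210 = 0.90 |
| 15 points | 0.14475/0.18525 = 0.78 | 0.185/0.215 = 0.86 |

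**Step 3: error rate and power.** Trials were simulated with a yes/no outcome of any opioid use, assumed at 30%, 50% or 70% in prior users and 5% in naive participants (8,000 trials per null scenario, 4,000 per power scenario). A crude two-proportion test was compared with a Cochran-Mantel-Haenszel test stratified by prior use.

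| Quantity | Crude | Stratified by prior use |
|---|---|---|
| Type I error over all randomisations | 5.2–5.3% | 5.0–5.5% |
| Type I error given 36 v 44 users | 5.5%, 6.9%, 6.1% | 4.7–5.5% |
| Type I error given 34 v 46 users | 8.0%, 12.4%, 16.6% | 4.8–5.5% |
| Power at a true relative risk of 0.7 | 15%, 25%, 33% | 17%, 29%, 47% |

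Triplets are in the order of the three assumed prior-user rates.

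**The case against.** The best defence is that prior use is already built into the outcomes that matter most. Both primary opioid outcomes are restricted by it, and the amendment text repeats the restriction for MME. Unequal numbers of users cannot bias a comparison made only among users or only among naive participants. Total MME and past-7-day use are limited to the naive. An unadjusted comparison of randomised groups is also valid, as the simulated 5.2–5.3% shows.

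All of this stands, and it rules out three stronger readings that a reader might infer:

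- *That prior opioid use plays no part in the opioid analysis.* Outcomes contradicts this. What is missing is the step from Outcomes to Statistical Methods. Nor are baseline factors wholly absent, since BMI enters one regression.
- *That the crude analysis is biased.* It is not, averaged over randomisations. The excess error exists only given an imbalance that has occurred.
- *That imbalance alone could produce the trial's 30% target.* That target belongs to the two primary outcomes; none is set for use days. Even taking 0.70 as a yardstick, imbalance alone reaches it only at about 22 points with 30% v 3% (0.3 × 0.165/(1.7 × 0.135) = 0.216), and about 35 points with 30% v 10% (0.3 × 0.20/(1.7 × 0.10) = 0.353).

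The assumed rates are also open to challenge. Prior opioids need not mean current use, and acute entrants had to be off opioids for the present episode. A smaller contrast between the groups would shrink the ratios in step 2 towards 1.

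The defence does not reach use days, which has no restriction, or the stratum, which no opioid method uses.

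**Conclusion.** The point holds in limited form. For the two primary opioid outcomes as defined, the only loss is the unused randomisation stratum. For use days, and for any MME or prescribing ratio run on all participants as Statistical Methods reads, chance imbalance in prior users is uncontrolled and precision is given up.

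On the assumed rates, an imbalance seen in roughly one randomisation in four moves the use-day ratio 10–15% away from 1, and one seen in roughly one in twelve moves it 14–22%, in either direction. The imbalance probabilities rest on the planned 160, equal arms and half prior users. The ratios, conditional error rates and power rest also on assumed use rates, so they show scale and do not predict this trial. Whether an imbalance arose can be read directly from the registration data. The flaw does not invalidate the trial, but it can be removed at little cost.

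**What to change.** 1. State in Statistical Methods which subset each opioid comparison uses, matching Outcomes. Define the paired MME set by baseline prior use, and reconcile the on-study-use definition with Outcomes and the 6/8/2022 amendment.
2. Within the naive and prior-user subsets, stratify or adjust by the acute/chronic stratum **as randomised**, not as reclassified by reported duration. Examples are a Mantel-Haenszel relative risk for naive prescribing, and a model with arm and stratum for MME change. A prior-use term is constant within these subsets, so it does not belong there.
3. For use days and any other pooled opioid comparison, use one record per participant and a model with arm, randomised stratum and baseline prior opioid use (yes/no). A log-link model with robust standard errors and completed diary days as the offset would suit use days. Add site only if it was recorded for each participant; Data Collection Methods does not list it.
4. Show prior-user counts by arm, and report the crude ratios beside the adjusted ones.
5. If these analyses were specified after enrolment, say so. The opioid methods are written in the past tense, so some results may already be known.

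The cost is SAP wording, a modest reanalysis of data in hand (the stratum and prior use are both recorded) and the post hoc label.
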